1 INTRODUCTION

Fluctuations in blood phenylalanine (Phe) concentrations may be an important determinant of intellectual outcome in patients with early and continuously treated phenylketonuria (PKU) (*Cleary et al, 2013*). Evidence suggests that physiological fluctuations in Phe concentrations in patients with PKU within a day are different to those seen in healthy individuals on a normal diet with an inverse diurnal variation (Phe concentrations higher in the morning) (*MacDonald et al 1998*). This suggests that protein catabolism predominates over protein anabolism during fasting periods (*Cleary et al, 2013*). In line with this, prolonged fasting results in a small rise in Phe concentrations with a peak in the early morning before breakfast (*MacDonald et al 2003*). The timing of protein substitutes also affects diurnal variation: distribution of protein substitute intake throughout 24 h stabilizes Phe concentrations (*MacDonald et al 1998, MacDonald et al 2003*). The median variation in plasma Phe concentrations was 155 µmol/L per day, with a minimum of 80 µmol/L and a maximum of 280 µmol/L, among 16 patients with classic PKU aged 1 to 18 years (*MacDonald et al 1998*).

The relationship between IQ and blood Phe levels is clear. However, only a few studies have specifically addressed Phe fluctuation and intellectual outcome and Phe concentrations and Phe fluctuations could not be separated with regard to their influence on IQ (*Cleary et al 2013*). Two studies have failed to determine this relationship between Phe fluctuations and cognitive impairment (*Anastasoiae et al 2008*). Phe concentrations build up in blood and brain and the ability to intrinsically produce the dopamine precursor tyrosine is lost. These changes do not solely affect the metabolism of dopamine. Also, reduced concentrations of noradrenaline and serotonin are found in PKU patients (on diet) and in the PKU mouse model (*Berguig et al 2019*).

PKU patients are a population at risk for sleep disorders due to deficits in neurotransmitter synthesis. Noradrenaline and serotonin neurotransmitters are known to be important regulators of sleep, wakefulness, and they move between these states. Analyses done on PKU mice and on PKU patients versus healthy people with 4 validated questionnaires confirmed sleep problems in PKU patients

(Bruinenberg *et al.* 2017). On the contrary, sleep disorders (using Bruni's Sleep Disturbance Scale for Children) were similar in both groups, 15.6% in control group and 12.5% in PKU group and no correlations were found with peripheral biomarkers of neurotransmitter synthesis melatonin and serotonin (Rosa Gassió, *et al.* 2019).

The aim of this randomised controlled study is to examine if by giving a slow-release protein substitute if it will reduce overnight catabolism in blood Phe levels and if this in turn will affect sleep patterns.

2 STUDY OBJECTIVES

2.1 Primary study objectives

- Reduce catabolic episodes during the night (measured by analysis of urine markers)
- Reduce peak Phe levels in the early morning (measured with 3 blood spots at 5:00, 6:00 and 7:00am before breakfast).
- Improved quality of sleep, associated with improved blood Phe level.

3 STUDY PARAMETERS

3.1 Primary study parameters

- Blood Phe after administration of PKU GOLIKE and after amino acid protein substitute as mean value of day 6 and 7 and day 27 and 28 of treatment based on 3 blood spots collected at 5:00, 6:00 and 7:00am before breakfast.

3.2 Secondary study parameters

- Tyr blood concentration with dried blood spots at 5:00, 6:00 and 7:00am before breakfast as mean value of days 6 and 7, and days 27 and 28 of treatment.
- Blood concentration of branch chain amino acids (BCAA) from dried blood spots at 5:00, 6:00 and 7:00am before breakfast as mean value of days 6 and 7, and days 27 and 28 of treatment.
- Urine sample to measure: urea and creatinine
- Quality of sleep (sleep questionnaire)
- Palatability of protein substitute Bars and Krunches (Palatability questionnaire)

- Adherence to the prescribed diet (use of product vs prescribed, as reported by the patient)
- Any side-effects (gastro-intestinal in particular—AE collection)

4 STUDY DESIGN

4.1 Study design

This is a 2 arm, randomised, controlled, cross-over study in 16 children with PKU. Subjects who are currently taking a Phe free/low Phe protein substitute will be recruited for a 31-day trial.

Patients will be randomised to receive:

- The study product for 7 days as their last dose of protein substitute for the day (at least 15g PE) in an amount equivalent to their usual protein substitute PE; or
- An amino acid protein substitute for all daily doses for 7 days;

followed by a 2-week washout period on their usual protein substitute, and then 7 days of the other study arm.

During this time, patients/caregivers will be asked to:

- Collect 3 finger prick blood spots on days -1, 0, 6, 7, 20, 21, 27 and 28.
- Collect urine sample, second void of the day on days 0, 7, 21 and 28.
- Complete a questionnaire on sleep quality on day 0, 7, 21 and 28.
- Complete a 24 hour food diary on days -1, 0, 6, 7, 20, 21, 27 and 28
- Palatability questionnaire on days 7 or 28 (at the end of the period with PKU GOLIKE, if Bars or Krunches are used)

APR will supply the study product for participants free of charge.

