5.2 Inclusion criteria

1. Male and female PKU patients ≥ 5 years and ≤ 16 years of age.
2. Patients diagnosed with PKU via new born screening.
3. Taking a Phe free/low Phe protein substitute
4. On a low phenylalanine diet .
5. Absence of neurological deficiencies.
6. Adherence with dietary management and protein substitute.
7. Able to understand and comply with the requirements of the investigation and sign the Informed Consent Form/Assent form.

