6 STUDY DESCRIPTION

6.1 Study description

Subjects who currently take a Phe-free/low Phe protein substitute (3 or 4 doses/day) will be recruited. Subjects will replace the last daily dose of their usual protein substitute with the study product for 7 days of the 28 day trial (either days 1-7 or days 22-28 based on random allocation). On the remaining study days, subjects will take an amino acid based protein substitute for all daily doses. There will be a 2 week washout period between study arms where subjects will take their usual protein substitute. The amount of study product prescribed will be calculated to provide the same amount of protein as their usual protein substitute. The last protein substitute (PS) dose of the day (amino acids or study product) will need to be taken between 7-9pm to allow an 8-10 hour fasting period overnight. Three finger prick blood spots will be collected and analysed for phenylalanine, tyrosine and BCAA at 5am, 6am and 7am on days -1, 0, 6, 7, 20, 21, 27 and 28. For the 16 subjects, a second void urine sample will be collected on days 0, 7, 21 and 28 for analysis of urea and creatinine. A quality of sleep questionnaire will be completed by subjects or their carers on days 0, 7, 21 and 28 and a 24 hour food diary on days -1, 0, 6, 7, 20, 21, 27 and 28. A palatability questionnaire will be completed by subjects or their carers on days 7 or 28 (at the

end of the period with PKU GOLIKE, if Bars or Krunches are used). Subject visits will be on days -2 (enrolment), 0, 7, 21 and 28 where the research dietitian will collect urine samples, blood spots, questionnaires and diaries.

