7 STUDY PROCEDURES AND ASSESSMENTS

7.1 Study procedures

Protein substitute administration

Patients will continue to take the same prescribed protein equivalent divided into 3 or 4 daily doses according to standard practice. The last daily dose of protein substitute (Test or Reference) will need to be taken between 7-9pm to allow an 8-10 hour fasting period before morning finger prick blood spots are taken. The study product will be taken as the last dose on either days 1-7 or days 22-28 (based on random allocation), with an amino acid protein substitute taken for the other doses on the same days. There will be a 2-week washout period on days 8-21 where subjects will take their usual protein substitute.

Finger prick blood samples

Routine weekly finger prick blood samples will continue to be collected by the subject or parent/caregiver and sent to the hospital laboratory for analysis of phenylalanine, tyrosine and BCAA as is usual clinical practice for these subjects. Additional blood spots will be required in week 1 and 4 (3 blood spots will need to be taken at 5am, 6am and 7am on days -1, 0, 6, 7, 20, 21, 27 and 28 of the study period).

Urine Samples

Subjects will be asked to record dietary intake on day -1 and use this same menu for all days before urine collection to ensure consistency of intake on urine collection days. Urine samples will be collected on each day of sampling. For 16 recruits a second void of the day urine sample will be collected. This will be frozen at home until collected by a research dietitian at the end of the study.

Sleep quality questionnaire:

A questionnaire on the quality of subject sleep will be completed by subjects/carers on days 0, 7, 21 and 28.

Palatability questionnaire:

A questionnaire on the palatability will be completed by subjects/carers on days 7 or 28 (at the end of the period of PKU GOLIKE administration, if Bars of Krunches have been used).

Diet and Activity Diary

A 24 hour food/fluid diary will be recorded on days -1, 0, 6, 7, 20, 21, 27 and 28.

Adherence:

Prescription details, amendments and intakes will also be recorded by the dietitian.

Concomitant medication:

All concomitant medications taken during the study will be recorded in the CRF with indication, dose information, and dates of administration. Permitted study medications will be those that in the opinion of the Investigator do not affect the subject's safety or interfere with the study procedures or outcomes.

STUDY FLOW CHART

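### The last-dose minimum and the usual-amount rule in 4.1 can conflict for a child whom 5.2 admits, and the number-of-doses condition in 6.1 is missing from the eligibility list

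*Protocol*

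**What the plan says.** Protocol 4.1 describes the study-product week. The product is the last dose of the day, and two conditions on its size stand side by side: "at least 15g PE) in an amount equivalent to their usual protein substitute PE". The comparator week is described as "An amino acid protein substitute for all daily doses for 7 days", with no minimum for any dose.

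Protocol 6.1 confines the substitution to one dose: "Subjects will replace the last daily dose of their usual protein substitute with the study product for 7 days of the 28 day trial". It then sets the quantity: "The amount of study product prescribed will be calculated to provide the same amount of protein as their usual protein substitute". It also states whom the trial recruits: "Subjects who currently take a Phe-free/low Phe protein substitute (3 or 4 doses/day) will be recruited".

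Protocol 7.1 speaks of the prescription as a whole: "Patients will continue to take the same prescribed protein equivalent divided into 3 or 4 daily doses according to standard practice".

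On the substitute itself, the inclusion list in 5.2 asks only for this: "Taking a Phe free/low Phe protein substitute". The age criterion is "Male and female PKU patients ≥ 5 years and ≤ 16 years of age". Neither 5.2 nor 5.3 mentions the number of daily doses, the size of the last dose or the total daily PE.

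**The concern.** A minimum and an equal-to-usual rule on the same dose are compatible only for children whose usual dose already reaches the minimum. The eligibility list does not restrict entry to those children, and the protocol gives no rule for the others. Whoever prescribes for such a child must either set one condition aside or change how the day's protein is divided.

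This bears on the primary parameter, which is blood Phe at 5, 6 and 7 am after a last dose taken between 7 and 9 pm. The protocol's own introduction says that the way substitute intake is spread over 24 hours affects the stability of Phe. Suppose the evening amount goes up in the study-product week to reach the minimum, and stays at its usual level in the amino acid week. The within-child difference then reflects evening amount as well as slow release. Randomising the order of the weeks does not remove this, because the extra evening protein goes with the product and not with the period.

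A second, separate gap is that the number of daily doses is a recruitment condition in 6.1 but not an item in 5.2. Someone screening from the list alone could enrol a child on 1 or 2 doses a day, whom 6.1 and 7.1 do not describe.

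**Working it through.** The plan has no figure of its own to reproduce here. The check is a comparison of sections plus simple arithmetic.

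**Inputs from the protocol.** Minimum last dose: 15 g PE (4.1). Number of daily doses, k: 3 or 4 (6.1, 7.1). Eligibility limit on last dose or daily PE: none (5.2, 5.3). Minimum in the amino acid week: none stated (4.1).

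**Inputs assumed.** Doses of equal size within a day, and daily totals T of 30 to 60 g PE for illustration. The protocol gives no prescriptions or body weights.

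**Step 1: usual amount read per dose.** The usual last dose is T/k. Both conditions hold only if T/k ≥ 15, that is T ≥ 15k:

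- 3 doses: 15 × 3 = 45 g a day
- 4 doses: 15 × 4 = 60 g a day

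Below these totals, a dose equal to usual is under the minimum, and a dose at the minimum is above usual.

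**Step 2: size of the gap.** The rise needed to reach the minimum is 15 − T/k, or 15/(T/k) − 1 in relative terms.

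| Assumed T (g PE/day) | Last dose, k = 3 | Rise to reach 15 g | Last dose, k = 4 | Rise to reach 15 g |
|---|---|---|---|---|
| 30 | 10.0 g | 5.0 g (50%) | 7.5 g | 7.5 g (100%) |
| 40 | 13.3 g | 1.7 g (12.5%) | 10.0 g | 5.0 g (50%) |
| 50 | 16.7 g | none | 12.5 g | 2.5 g (20%) |
| 60 | 20.0 g | none | 15.0 g | none |

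**Step 3: usual amount read as the daily total, as in 7.1.** Any T of at least 15 g can satisfy both conditions if the remaining doses become (T − 15)/(k − 1). For T = 40 and k = 4 this is (40 − 15)/3 = 8.3 g, so the day changes from 4 × 10.0 g to 15 + 3 × 8.3 g. The total is preserved, but 5.0 g has moved from daytime to evening.

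**Step 4: compare the two weeks.** If the amino acid week keeps the usual split, the child in step 3 takes 15 g in the evening of one week and 10 g in the other. The products then differ in evening amount as well as in release. If the same redistribution is made in both weeks, the amounts match. The protocol requires neither.

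**Step 5: number of doses.** Sections 6.1 and 7.1 both specify 3 or 4, and 5.2 and 5.3 are silent. This gap is independent of steps 1 to 4: a child on 3 or 4 doses can still have a last dose under 15 g.

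**The case against.** The best defence reads the 15 g in 4.1 as describing the last dose that participants already take, with the study product then matched to it. On that reading 4.1 does not contradict itself. The wording allows this, but the 15 g then acts as an entry condition, and it is still missing from 5.2. The remedy is the same.

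It can also be said that the number of doses is stated in 6.1 and repeated in 7.1, and that inclusion criterion 7 requires the child to be able to comply with the investigation. This is right as far as it goes: the condition is in the protocol and nothing in 5.2 contradicts it. It is only missing from the list used to decide entry.

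The objection that no magnitude has been shown also stands. The thresholds rest on equal doses, and the daily totals in the table are illustrative.

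A reader might infer more than the text supports:

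- That 7.1 also makes the conditions impossible to meet together. It does not: it fixes the prescribed protein over the day, which can be kept by redistribution.
- That the missing dose number causes the conflict over the minimum. It does not. With a fixed total and equal doses, fewer doses make a last dose under 15 g less likely.
- That the youngest children are the ones affected. The protocol gives no prescriptions by age.
- That different sites would enrol different children. Section 5.1 names one centre.
- That evening protein will differ between the weeks. The protocol does not say so; it only fails to prevent it.

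**Conclusion.** The point holds in a limited form. On the per-dose reading, which fits best with 6.1 because only the last dose is replaced, a child whose usual last dose is below 15 g PE is eligible under 5.2 but cannot meet both conditions in 4.1. On the daily-total reading, that child can meet both only by shifting protein to the evening, and nothing in the protocol holds the evening amount equal in the amino acid week. Either way, the primary Phe contrast may carry a difference in amount for the children concerned.

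Under equal doses, the children concerned are those below 45 g PE a day in 3 doses or below 60 g in 4. How many of the 16 that would be, and how far their Phe would move, cannot be determined from the protocol. The absence of the dose-number condition from 5.2 is a separate and smaller inconsistency.

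**What to change.** The sponsor should reconcile 4.1, 5.2, 6.1 and 7.1 on the amount of the last dose and on the number of daily doses. The text should say whether the usual amount refers to the last dose or to the daily total, and how the 15 g figure relates to it. Two results are needed: every child who is eligible under 5.2 can follow the schedule as written, and the evening protein amount does not differ between a child's two treatment weeks. Any entry condition that follows, including the number of doses, should be added to 5.2. How the minimum and the usual amount are reconciled is for the sponsor to decide.

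The cost is a few lines of text, best settled before enrolment. If the minimum becomes an entry condition, the eligible pool at the single centre shrinks by an amount that the protocol does not allow one to estimate.

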5 SUBJECTS

5.1 Study population

16 children, diagnosed with PKU requiring a low phenylalanine diet will be recruited from one specialist PKU centre.

5.2 Inclusion criteria

1. Male and female PKU patients ≥ 5 years and ≤ 16 years of age.
2. Patients diagnosed with PKU via new born screening.
3. Taking a Phe free/low Phe protein substitute
4. On a low phenylalanine diet .
5. Absence of neurological deficiencies.
6. Adherence with dietary management and protein substitute.
7. Able to understand and comply with the requirements of the investigation and sign the Informed Consent Form/Assent form.

5.3 Exclusion criteria

1. Age < 5 years old and > 16 years old.
2. Patients with mild PKU or HPA.
3. On sapropterin therapy.
4. Patients with late diagnosis of PKU and neurological problems.
5. History of hypersensitivity to any excipients/components of the investigational product.
6. Pregnancy or breastfeeding during the study.
7. Any moderate to severe acute illness which in the opinion of the Investigator would interfere with the study procedures or study outcome.
8. History of poor co-operation, non-adherence with dietary management, or poor adherence to investigation procedures.
9. Participation in any other studies involving investigational or marketed products concomitantly or within two weeks prior to entry into the study.

5.4 Subject recruitment

16 children with PKU will be recruited. When an appropriate subject has been identified, they and their parents/caregivers will be sent a study information sheet via the post. They will be invited to request further information about the study if they wish by contacting the Dietitian. The Dietitian will explain the study in more detail either by telephone or via a face-to-face consultation in a

convenient location/pREFERRED venue for the participant and their parent/caregiver. Recruitment of each patient will be by written informed consent, which will be completed by the parents/primary caregivers and taken by the Dietitian. Children will also complete an assent/consent form. Reimbursement will be offered for any travel expenses incurred for any visits to the hospital that are over and above normal/routine visits.

REPLACEMENT/NON-ADHERENT PATIENTS

Patients that are not compliant or need to be excluded for other clinical reasons to the treatment schedule will be replaced in order to obtain 16 complete subjects per treatment group. This procedure is according to cross-over design in order to have a complete matrix of data.

URINE COLLECTION

For the 16 children recruited, a second void of the day urine sample will be collected on days 0, 7, 21 and 28 to analyse for urea and creatinine. These will be frozen at the patients home (containers will be provided) and collected at the end of the study.

6 STUDY DESCRIPTION

6.1 Study description

Subjects who currently take a Phe-free/low Phe protein substitute (3 or 4 doses/day) will be recruited. Subjects will replace the last daily dose of their usual protein substitute with the study product for 7 days of the 28 day trial (either days 1-7 or days 22-28 based on random allocation). On the remaining study days, subjects will take an amino acid based protein substitute for all daily doses. There will be a 2 week washout period between study arms where subjects will take their usual protein substitute. The amount of study product prescribed will be calculated to provide the same amount of protein as their usual protein substitute. The last protein substitute (PS) dose of the day (amino acids or study product) will need to be taken between 7-9pm to allow an 8-10 hour fasting period overnight. Three finger prick blood spots will be collected and analysed for phenylalanine, tyrosine and BCAA at 5am, 6am and 7am on days -1, 0, 6, 7, 20, 21, 27 and 28. For the 16 subjects, a second void urine sample will be collected on days 0, 7, 21 and 28 for analysis of urea and creatinine. A quality of sleep questionnaire will be completed by subjects or their carers on days 0, 7, 21 and 28 and a 24 hour food diary on days -1, 0, 6, 7, 20, 21, 27 and 28. A palatability questionnaire will be completed by subjects or their carers on days 7 or 28 (at the

end of the period with PKU GOLIKE, if Bars or Krunches are used). Subject visits will be on days -2 (enrolment), 0, 7, 21 and 28 where the research dietitian will collect urine samples, blood spots, questionnaires and diaries.

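### Does rating sleep on the second of two 5am sampling mornings call for a change to the schedule?

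*Protocol*

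**What the plan says.** Three sections of the protocol give the same sleep-rating days. Section 4.1 lists "Complete a questionnaire on sleep quality on day 0, 7, 21 and 28", section 6.1 has "A quality of sleep questionnaire will be completed by subjects or their carers on days 0, 7, 21 and 28", and section 7.1 has "A questionnaire on the quality of subject sleep will be completed by subjects/carers on days 0, 7, 21 and 28".

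Section 6.1 schedules blood spots "at 5am, 6am and 7am on days -1, 0, 6, 7, 20, 21, 27 and 28". The last protein substitute of the day "will need to be taken between 7-9pm to allow an 8-10 hour fasting period overnight". Visits are on days -2, 0, 7, 21 and 28, "where the research dietitian will collect urine samples, blood spots, questionnaires and diaries".

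Sleep is a primary objective in section 2.1 ("Improved quality of sleep, associated with improved blood Phe level") but a secondary parameter in section 3.2. The only primary parameter, in section 3.1, is early-morning blood Phe. The flow chart calls the sleep questionnaire validated. The document does not name the instrument or give its recall period.

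**The concern.** Three finger pricks between 5am and 7am will probably wake a child aged 5 to 16, or the carer. Every sleep rating is made on the second such morning in a row. If the questionnaire asks about last night or the last two nights, every rated night ended in a disturbance caused by the trial. A real difference between products could then be blunted or lost in noise. A null sleep result in 16 children would be hard to interpret, and with so short a recall no analysis could recover ratings of undisturbed nights.

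Allowing subjects or their carers to complete the form also leaves open who rates a given child on each occasion. An obvious remedy suggests itself: have the form completed just before each sampling block, on days -2, 5, 19 and 26.

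**Working it through.** The protocol states no power or effect size for sleep, so there is no figure of its own to reproduce. The check is a count of days, followed by an illustration on stated assumptions.

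**Overlap.** Sampling mornings (section 6.1) form the pairs (-1, 0), (6, 7), (20, 21) and (27, 28). Rating days are 0, 7, 21 and 28. All 4 of 4 ratings fall on the second day of a pair.

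**On-product nights.** The last dose is taken in the evening, from day 1 or day 22. The mornings that follow a dose of the period, up to the rating, are therefore 2 to 7 or 23 to 28: six nights, of which 2 (33%) end in sampling.

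**Share of rated nights ending in 5am sampling, by recall length (assumed, since none is stated).** The share is sampled nights divided by recall nights.

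| Recall (nights) | Days 0 and 21 | Days 7 and 28 |
|---|---|---|
| 1 or 2 | 100% | 100% |
| 3 | 2/3 = 67% | 67% |
| 4 | 2/4 = 50% | 50% |
| 6 | 2/6 = 33% | 33% |
| 7 | 2/7 = 29% | 29% |
| 14 | 2/14 = 14% | 4/14 = 29% |

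At 28 nights the share runs from 2/28 = 7% to 6/28 = 21%.

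**Direction.** Write a child's rating in a period as product effect + disturbance + error. If the disturbance is the same in both periods, it drops out of the within-child difference. Only a disturbance that shrinks the product contrast or adds variance does harm.

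**Possible size.** Let w be the share of the product contrast lost on a sampled night (assumed, 0 to 1). Over six nights the contrast kept is 1 - (2/6)w = 1 - w/3. A two-sided paired t-test with n = 16 and alpha 0.05 has 80% power at a standardised effect of 0.749 (the 80% is also an assumption).

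- w = 0: factor 1, power 80%.
- w = 0.5: factor 0.833, power 65%.
- w = 1: factor 0.667, power 46%.

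The range from 46% to 80% reflects the assumed range of w and nothing in the protocol. Period and sequence terms are ignored.

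**Moving the ratings to days -2, 5, 19 and 26.**

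- Recall of 1 to 4 nights: no sampled night at any rating. In the treatment periods every rated night follows a dose of that period.
- Recall of 5 nights on day 5 (mornings 1 to 5) or day 26 (22 to 26): 1 off-product night.
- Recall of 6 nights (mornings 0 to 5, or 21 to 26): 2 off-product nights, 1 of them sampled.
- Recall of 7 nights (mornings -1 to 5, or 20 to 26): 3 off-product nights, 2 of them sampled.

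**Shortening a six-night recall to four so that the move works.** Let s be the share of rating noise that is independent from night to night. The standardised effect is multiplied by 1/sqrt(1 - s + 1.5s), where 1.5 = 6/4. The move breaks even when 1 - w/3 equals this factor, so w = 3(1 - factor).

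| s | Factor | Power | Break-even w |
|---|---|---|---|
| 0 | 1.000 | 80% | 0 |
| 0.25 | 0.943 | 75% | 0.17 |
| 0.5 | 0.894 | 71% | 0.32 |
| 0.75 | 0.853 | 67% | 0.44 |
| 1 | 0.816 | 63% | 0.55 |

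The document gives neither s nor w, so it does not show whether the move would gain or lose power.

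**The case for a change.** The strongest case for acting is that sleep stands among the primary objectives, the clash is of the trial's own making, and rating days and sampling times are fixed in the protocol rather than left to a later analysis plan. A validated form may still ask only about last night. The move would need no extra forms or visits: day -2 is already a visit, and families already keep a "24 hour food diary on days -1, 0, 6, 7, 20, 21, 27 and 28", which includes days without a visit. With a recall of one to four nights it removes every sampled night without reducing the number of nights rated.

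The overlap and the plausibility of some disturbance stand. The case for rescheduling does not, because of what the move gives up:

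- The objective in section 2.1 ties sleep to blood Phe. The present dates rate sleep on the mornings when Phe is measured; the alternative uses adjacent nights.
- The present dates include the two nights with the longest exposure in each seven-day period; the alternative leaves them out.
- The present baselines, days 0 and 21, match: each follows two sampled nights within the study. On day -2, the enrolment visit, every rated night would precede consent, while day 19 falls in mid-trial.
- Setting a validated instrument to a shorter recall could affect its validation.

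For recalls of five nights or more the move takes in off-product nights, so the dates are better left alone. Stating the recall period and keeping one respondent per child would be useful, but these are details of the instrument and its administration that the study team can settle within the plan. The protocol states no change of rater, and allowing child or carer to answer suits the age range of 5 to 16.

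**Conclusion.** No change to the plan is needed. All four ratings do fall on the second of two sampling mornings, but the sampling load is the same in both periods and at both baselines. The comparison is not tilted towards either product. The possible cost is lost sensitivity on sleep, a secondary parameter, and it cannot be sized from the protocol: from 1 to 28 nights of recall, sampled nights make up 100% down to 7% of those rated.

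The current dates are a fair trade-off: they accept some disturbance in return for ratings that coincide with the Phe measurements and the end of each treatment week. The alternative helps only if the recall is one to four nights, and even then it gives up those two advantages. If six nights had to be cut to four, it would gain power only when w exceeds a threshold between 0 and 0.55.

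This conclusion rests on the sampling being carried out alike in both periods, as scheduled. A null sleep result should be read with the instrument's recall period in view.
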